This practice of direct bonding could yield inaccurate placement of even perfectly positioned and contoured brackets created using a digital treatment program. To solve this issue, LFO created a 3D printed patient-specific indirect-bonding (IDB) system. Designed directly from the desired bracket placement on the teeth in malocclusion, like a digital mold, the IDB tray precisely matches the tooth anatomy and brackets. Once printed, the corresponding patient's brackets are placed in the IDB tray's bracket wells. The orthodontist can paste the bonding material onto the brackets, while remaining in their specific wells, then place the IDB trays in the patient's mouth and bond the brackets. Once the tray is removed the brackets remain on the teeth in the exact position they were designed for in the treatment planning system.

The presented investigational testing aims to assess treatment efficiency metrics using the LightForce Orthodontic system on a variety of malocclusions across multiple sites compared to the investigator's past experience using traditional bracket systems.

Investigation Design & Participants

This multi-site investigation will evaluate treatment efficiency metrics of different orthodontists using the same LightForce Orthodontic digital treatment planning system and patient-specific brackets. Data collection will include treatment efficiency metrics, participant data such as (but not limited to) gender, age and medical history, and experiential data of standard bracket treatment efficiency metrics. Efficiency metrics may include:

- Treatment length
- Bonding/De-bonding appointment time length
- Length of time to achieve leveling and alignment
- Number of unscheduled appointment
- Number of debonded brackets
- Number of repositioned brackets

All patients that visit the investigation sites are evaluated during initial consultations for their particular medical needs and orthodontic treatment. If a patient is eligible for the investigation, they will be presented with the treatment plan, asked whether they would like to participate, and given a consent form to sign.

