The LightForce Orthodontic braces are commercially available in the United States. Every orthodontist in this study will pay LightForce Orthodontics for the LFO System as they would if they were available to purchase in Canada. As such there is no conflict of interest.

However, some investigators are a part of the LightForce Orthodontics' clinical executive board (CEB). If so a [CEB Appendix](#) is attached to their patient's consent form. To also combat any undue influence conflict of interests may have on this study, the investigators chosen are a mix of CEB and non-CEB members. This means any CEB member's data should not influence the overall study

results.

Statistical Analysis

Statistical tests (Student's t-test) will be run to make sure LightForce Orthodontics's Clinical Executive Board (CEB) member treatment group outcomes are not statistically different from non-CEB members within this study. If they are, the data collected from that investigation site will be removed.

We will assume the data will be normally distributed for this study. The primary outcome measures are impacted directly by the patient's age and by the treating orthodontists. Thus the outcome variables will be analyzed through analysis of covariance (ANCOVA) tests controlling for age and orthodontist. Multiple pair wise comparisons may be conducted (t-tests) to determine significant differences between groups. Bonferroni corrections may be conducted to prevent the introduction of Type 1 errors. Multivariate linear regressions may also be used to examine differences in the treatment groups. All statistical tests will be two-sided with a p-value of 0.05 for statistical significance. All statistical analyses will be conducted in a statical software such as SAS software (SAS Institute, Cary, NC).

Risk Assessment

There are no additional risks to participating in this study outside of the standard risks associated with orthodontic treatment. The study does not change the standard method of diagnosis and care for the treatment of malocclusion. The LFO bracket system has been approved by the FDA and is comparable to existing bracket systems. During the approval process, the device underwent standard orthodontic bracket performance tests compared to commercially available devices and biocompatibility tests. These reports can be made available upon request.

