Each system is shipped with an instructions for use which contains the following precautions - there are no known adverse reactions or contraindications for this device:

- Due to the hardness of ceramic brackets, bonding brackets in occlusion should be avoided to prevent wearing of enamel surfaces during all phases of treatment.
- LightForce Orthodontic Brackets can withstand all normal torque requirements. However, care should be taken when making torquing activations. Large corrections with full size stainless steel wires may result in bracket failure and should be avoided.
- Instruct not to chew or bite hard substances such as hard candy, ice, or carrots. Careful and thorough patient instruction is key to avoiding appliance or enamel damage.
- LightForce Orthodontic Ceramic Brackets should be avoided in bonding to dental porcelain, restorative or compromised (i.e. large restorations, peg laterals, or pre-existing pathological conditions) enamel surfaces.
- Bonding to porcelain crowns or facings may cause chipping or breakage of the crown or facing during treatment or debonding.

- LightForce Orthodontic Ceramic Brackets are for single patient use only.

Data Monitoring and HIPAA Privacy Protections

All data taken during this study is apart of normal data acquisition for an orthodontic treatment. Each patient will be given a patient alias number. The LFO treatment representative will see identifying information regarding patients but will only record the patient's alias and relevant information for the study. The data collected will not directly link back to the participant's identity which minimizes the risk of a confidentiality breach. Experiential data will be acquired by LFO via communication with the orthodontist. All information is kept on password protected computers and servers. No paper print outs are kept in this study. The signed consent forms are scanned and sent back to LFO through secure emails. The orthodontist can then shred the forms. All personnel involved in this study as well as all members of LightForce Orthodontics are trained on Health Insurance Portability and Accountability Act (HIPAA) privacy rules. The investigators have all been trained on human subjects' research.

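### The conflict-of-interest check, on its natural reading, compares only LFO outcomes by board membership, so it cannot respond to distortion of the traditional-bracket figures that the same orthodontists relay

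*Combined protocol and SAP*

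**What the plan says.** All references are to the combined protocol and SAP.

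- **Who is treated with what.** Investigation Design & Participants says the study evaluates "treatment efficiency metrics of different orthodontists using the same LightForce Orthodontic digital treatment planning system and patient-specific brackets". There is no concurrent traditional arm.
- **The comparator.** The end of the Significance text sets LFO results "compared to the investigator's past experience using traditional bracket systems". Investigation Design & Participants lists the comparator data as "experiential data of standard bracket treatment efficiency metrics", separately from the metrics of the enrolled patients.
- **How the comparator arrives.** Data Monitoring and HIPAA Privacy Protections: "Experiential data will be acquired by LFO via communication with the orthodontist". No verification of the relayed figures against records is described.
- **The assurance.** Conflicts of Interest states that the investigators are a mix of CEB and non-CEB members, and continues: "This means any CEB member's data should not influence the overall study" results.
- **The check.** Statistical Analysis: "Statistical tests (Student's t-test) will be run to make sure" CEB "member treatment group outcomes are not statistically different from non-CEB members within this study". The consequence is: "If they are, the data collected from that investigation site will be removed".
- **The main analysis.** The same section plans an ANCOVA adjusted for age and orthodontist, two-sided at 0.05.

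**The concern.** The check and the study's result are about different quantities. The result is a contrast between LFO and traditional brackets within orthodontist. The check looks at the level of outcomes inside the study, where every patient has LFO. If a CEB member relays traditional values that are too unfavourable, for example treatment times that are too long, no LFO value changes. The check gives the same answer as it would have given without the distortion, while the contrast shifts in favour of LFO.

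This is not a matter of low power. More patients would not make the check sensitive to data that it does not use. Adjusting for orthodontist does not help either, because the distortion lies within orthodontist, between that orthodontist's two sets of values. At stake is whether a passed check says anything about the half of the comparison that conflicted investigators supply themselves.

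**Working it through.** **The plan's own figure.** The only sample-size figure is 22 patients per site for 90% power at the 5% level. It cannot be reproduced, because no effect size or SD is given. The point does not depend on it; 22 is used below only as a site size.

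**Inputs not in the documents (assumptions).** Outcomes are normal with SD 1. There are K orthodontists, half of them CEB, each with 22 LFO and 22 patient-level traditional values. There is no true bracket effect, CEB traditional values are overstated by b SD, and no site is removed. The age term is left out.

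**Step 1: the check.** The statistic is the mean CEB LFO outcome minus the mean non-CEB LFO outcome. The quantity b does not appear in it. In simulation (8,000 runs per setting; K = 2, 4, 6; b = 0, 0.25, 0.5, 1.0) it triggered in 4.5% to 5.4% of runs, with no trend in b.

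That level holds only if orthodontists do not differ. For K = 4, with an assumed between-orthodontist SD of 0.3 or 0.5, the trigger rate is about 24% or 41%. It is still unrelated to b.

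**Step 2: bias in the bracket difference.** With equal site sizes, bias = CEB share × b.

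- b = 0.25: 0.5 × 0.25 = 0.125 SD
- b = 0.5: 0.5 × 0.5 = 0.25 SD
- b = 1.0: 0.5 × 1.0 = 0.50 SD

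**Step 3: false-positive rate, K = 4.** Each bracket has 4 × 22 = 88 values, so SE = √(2/88) = 0.151.

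- b = 0.5: 0.25/0.151 = 1.66 standard errors, so a rate of about 38% by normal approximation and 37% by simulation.
- b = 0.25: 0.125/0.151 = 0.83 standard errors, so about 13% by either method.

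By number of orthodontists at b = 0.5 (simulation): 20% (K = 2), 37% (K = 4), 53% (K = 6).

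**Step 4: what other comparisons would see at b = 0.5 (simulation).**

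| Comparison, CEB v non-CEB | K = 2 | K = 4 | K = 6 |
|---|---|---|---|
| LFO outcomes (natural reading of the plan) | 5% | 5% | 5% |
| LFO-minus-traditional difference | 20% | 37% | 53% |
| Traditional figures alone | 36% | 64% | 82% |

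For K = 4 the second row can be checked by hand. Each orthodontist's difference has variance 2/22. The mean over two orthodontists has variance 1/22, and the CEB minus non-CEB contrast has variance 2/22, so SE = 0.302. Then 0.5/0.302 = 1.66, the same ratio as in step 3.

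**Step 5: the assurance.** Since bias = share × b, adding non-CEB investigators lowers the share and so dilutes the bias. The bias is zero only when the share or the distortion is zero.

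**The case against.** Several objections have force, and some limit what can be claimed.

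- **The scope of the check is not spelled out.** A reader might infer that the plan expressly limits the check to LFO outcomes. It does not: the term for the group compared is undefined, and the plural is used later in the section for the groups under comparison. LFO-only is the natural reading, given the singular, the restriction to this study and the fact that all enrolled patients have LFO. On any reading, no text says that the relayed traditional figures are tested.
- **The trigger rate need not be 5%.** A reader might infer a fixed 5% rate. The plan itself says that outcomes depend on the treating orthodontist, so the rate could be well above 5%, and each trigger removes site data. What stands is that the rate does not respond to comparator distortion.
- **The plan does not rest its assurance on the t-test.** The statement that CEB data should not influence results follows from the mix of investigators, in a different section. It has to be judged as a separate claim, and it fails because a mix only dilutes.
- **Patient-level traditional data are not established.** The documents may mean one summary figure per orthodontist. The simulated rates and a patient-level interaction term would then not apply.
- **A CEB difference is not proof of bias.** It could be genuine, for example if CEB members are more practised with LFO. Overstatement shared by both groups would cancel out of the comparison and stay hidden.
- **Nothing shows that distortion took place or is likely.** That objection is right; the documents show only that it would go undetected.

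**Conclusion.** The point holds in this form: the plan does not state any check by CEB status on the traditional figures or on the LFO-minus-traditional difference, and the check that it does state, read naturally, cannot respond to distortion of the comparator. That conclusion is structural and needs no assumed number.

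Its size does. The bias is CEB share times distortion. The 0.25 SD bias and 37% false-positive rate belong to one illustration (four orthodontists, half CEB, 0.5 SD overstatement, patient-level data, no site removal). The documents give no number of sites, CEB share, SD or plausible size of distortion.

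Separately, the statement that a mix of investigators means CEB data should not influence the results does not follow. The documents do not support reading this as evidence that CEB members misreported.

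**What to change.** 1. In Statistical Analysis, apply the CEB v non-CEB comparison to the within-orthodontist LFO-minus-traditional difference. If patient-level traditional data are obtained, add a bracket-by-CEB term to the ANCOVA. If only one summary per orthodontist is available, compare the site-level differences between the two groups.
2. Report it as an estimate with a 95% confidence interval, not as a pass/fail rule.
3. Show the bracket effect with and without CEB sites.
4. State which data the existing check covers. Showing the traditional figures themselves by CEB status is a useful addition.
5. In Conflicts of Interest, delete the inference that a mix of investigators prevents influence.

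**Cost.** SAP wording and, where patient-level traditional data exist, one model term. If they do not, only the site-level comparison is available without collecting more data. The estimate will be imprecise with few orthodontists: about 37% detection in the illustrated case, and only 2 + 2 − 2 = 2 degrees of freedom if four site summaries are all there is. It cannot separate reporting bias from a genuine difference, it does not detect overstatement common to both groups, and it describes a bias without removing it.

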There are no specific recruitment materials for this study. However, each orthodontist is provided with a LightForce Orthodontics welcome kit before they enroll their first patient. This includes a typodont, a sample product package (box, brackets in trays and arch form) and patient brochures as pictured below. The patient brochures are not included as study recruitment material.

To run statistical analysis, at least 22 patients must participate at each investigation site to have a power of 90% at a 5% significance level. No patients will be withdrawn from the investigation unless the investigator or patient chooses to discontinue treatment. If there is a lack of compliance with the investigator's treatment plan and/or a developing health condition during treatment, the patient's data may be considered an outlier and not used in statistical analysis.

Inclusion Criteria

- All subjects must be healthy and between the ages of 10 and 65.
- Eruption of all permanent teeth excluding second and third molars
- Sufficient labial tooth surface for bonding
- No more than one tooth missing from a single arch quadrant
- No existing molar tubes or bands

Exclusion Criteria

- Presence of systemic diseases, cleft lip and palate, craniofacial anomalies, syndromes affecting bone or teeth, impacted teeth (excluding 3rd molars), and tumors of the parathyroid gland
- Presence of bridges or implants
- Cases requiring orthognathic surgery
- Significant periodontal disease
- Intake of drugs affecting tooth movement or bone formation (chronic use of Non-Steroidal Anti Inflammatory Drugs, bisphosphonates, levothyroxine, or teriparatide drug class)
- Pregnancy

Clinical Process

Orthodontic treatment process through out this investigation will follow standardized practices. Treatment data will be acquired throughout the following process:

- Facial photos and intra-oral scans will be taken of the patient's teeth
- Treatment will be planned using the LightForce Orthodontics' LF Pro treatment planning system
- LightForce Orthodontics will manufacture and ship the patient-specific brackets to the investigator
- Standard Orthodontic Treatment Progressions
 - Brackets will be bonded to patient's teeth
 - Follow up appointments to change ligatures, move through standard wire progression, and/or replace brackets. The number of appointments can vary based on the patient's treatment plan and progress.
 - Brackets are removed

Conflicts of Interest

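### Mandatory removal of site data after a significant CEB versus non-CEB t-test can discard sound sites, and a non-significant test does not show that CEB influence is absent

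*Combined protocol and SAP*

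**What the plan says.** The Conflicts of Interest section discloses that some investigators sit on the sponsor's clinical executive board. It states that "the investigators chosen are a mix of CEB and non-CEB members" and concludes from this that "any CEB member's data should not influence the overall study" results.

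The Statistical Analysis section then sets a check. Student's t-tests are to ensure that CEB "member treatment group outcomes are not statistically different from non-CEB members within this study". The consequence of a significant result is mandatory: "If they are, the data collected from that investigation site will be removed". For this check the plan names no outcome, unit of analysis, covariate or margin, and it describes no analysis that keeps the removed sites.

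The next paragraph says: "The primary outcome measures are impacted directly by the patient's age and by the treating orthodontists". For that reason the outcome analysis uses ANCOVA controlling for age and orthodontist. Neither this adjustment nor the optional Bonferroni correction is tied to the CEB check. The general rule on significance does apply: "All statistical tests will be two-sided with a p-value of 0.05 for statistical significance".

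**The concern.** Whether a site stays in the data depends on that site's outcomes, through a test that is not suited to the decision. There are three faults.

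1. **The trigger responds to ordinary differences between orthodontists.** CEB status is a property of the orthodontist, and the plan itself says that orthodontists affect outcomes. A patient-level t-test treats patients of one orthodontist as independent, so it triggers too often even when CEB membership has no effect. A test on site or orthodontist means holds its level but has little power with few sites. Age is a second possible route to a false trigger, of unknown size, since eligibility is wide: "All subjects must be healthy and between the ages of 10 and 65".
2. **Non-significance is read as absence of a difference.** The test is meant to establish that CEB outcomes do not differ. A non-significant t-test cannot establish that.
3. **The site to be removed is not identified.** A comparison of two groups does not single out one site once there is more than one CEB site.

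At stake are the loss of sound sites (a pooled analysis loses precision, and a per-site analysis loses that site's result) and false reassurance about a declared conflict of interest. No inflation of p-values or bias in the custom-versus-traditional comparison is claimed.

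**Working it through.** **Inputs from the plan.** Two-sided 0.05 (Statistical Analysis); "at least 22 patients must participate at each investigation site" (Investigation Design & Participants); Student's t-test with no stated adjustment.

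**Assumptions, because the plan gives no figures.** ICC between orthodontists 0.01 to 0.20; one to five sites per group; a true CEB difference of 0, 0.3 or 0.5 SD; exactly 22 patients per site; one outcome; normal data with total SD 1. Simulated rates use 40,000 trials per cell.

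The plan gives no operating figure for this check, so there is none to reproduce.

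**Step 1. False triggers, patient-level test, no CEB effect.** Clustering multiplies the variance of a group mean by 1 + (22 − 1) × ICC. The trigger rate is then roughly 2 × {1 − Φ(1.96 / √(1 + 21 × ICC))}. At ICC 0.05 the factor is 2.05, 1.96 / √2.05 = 1.369, and the rate is 0.171.

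| ICC | 1 + 21 × ICC | Approximate rate | Simulated rate |
|---|---|---|---|
| 0.01 | 1.21 | 0.075 | 0.072-0.076 |
| 0.05 | 2.05 | 0.171 | 0.172-0.178 |
| 0.10 | 3.10 | 0.266 | 0.269-0.283 |
| 0.20 | 5.20 | 0.390 | 0.398-0.431 |

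The simulated ranges cover 1v1, 2v2, 3v3, 5v5, 2v4 and 1v3 sites. At ICC 0 the rate is 0.048-0.050, as it should be. More sites do not cure the inflation.

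**Step 2. Missed differences at ICC 0.05 (1 minus the trigger rate).**

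| Test, true difference | 1v1 | 2v2 | 3v3 | 5v5 |
|---|---|---|---|---|
| Patient level, 0.3 SD | 1 − 0.275 = 0.725 | 1 − 0.363 = 0.637 | 1 − 0.442 = 0.558 | 1 − 0.574 = 0.426 |
| Patient level, 0.5 SD | 1 − 0.426 = 0.574 | 1 − 0.603 = 0.397 | 1 − 0.738 = 0.262 | 1 − 0.890 = 0.110 |
| Site means, 0.3 SD | not possible | 1 − 0.093 = 0.907 | 1 − 0.157 = 0.843 | 1 − 0.276 = 0.724 |
| Site means, 0.5 SD | not possible | 1 − 0.166 = 0.834 | 1 − 0.339 = 0.661 | 1 − 0.624 = 0.376 |

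The site-means test has total sites minus 2 degrees of freedom, hence none at 1v1. Its false-trigger rate is 0.048-0.052. At 5v5 the patient-level test detects even 0.3 SD more often than not, so the risk of false reassurance depends strongly on the number of sites.

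**Step 3. Precision lost on removal.** With equal sites, the pooled CI widens by √(sites before / sites after). Removing 3 of 6 gives √(6/3) = 1.41; 2 of 6 gives √(6/4) = 1.22; 1 of 6 gives √(6/5) = 1.10.

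**The case against.** The strongest objection concerns what counts as a false trigger. The plan asks whether outcomes differ within this study and makes no claim about a wider population of orthodontists. If the null is that the chosen CEB sites and the chosen non-CEB sites have equal means, the patient-level test triggers about 3-5% of the time and is not inflated. This is correct, and the rates in Step 1 apply only when the question is whether CEB status itself matters. That is the question a conflict-of-interest check must answer, and an unadjusted test cannot separate CEB status from the individual orthodontist under either null.

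Second, the singular wording may mean that each CEB site is compared with the non-CEB sites and dropped if it differs. The third fault would then largely fall away. The plan does not say this, so the ambiguity stands. On that reading the loss can be as small as 1.10-fold. The misses remain: for one CEB site against three or five others at ICC 0.05, a patient-level test misses 0.3 SD about 69% or 67% of the time, and 0.5 SD about 48% or 45%.

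Third, dropping CEB sites may be called conservative, and the power statement is per site, so losing one site does not weaken the others. Both points limit the damage. If exclusion is wanted, though, it can be fixed in advance, without a noisy test making the choice.

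**Conclusion.** The concern holds and should be fixed. The plan sets a mandatory removal rule triggered by outcomes, and its test ignores the sources of variation named in the paragraph that follows it.

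A patient-level test triggers wrongly about 7-8% to 40-43% of the time over ICC 0.01 to 0.20. A site-means test avoids this but at ICC 0.05 misses 0.5 SD between 38% (5v5) and 83% (2v2) of the time. These sizes rest on assumed ICCs, site counts and differences. Three conclusions need none of those values: a significant t-test cannot attribute a difference to CEB status, a non-significant one cannot show that there is no difference, and a two-group result does not name a site.

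The consequence is limited to lost precision or a lost site result, and to false reassurance about CEB influence.

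**What to change.** Delete the removal rule and replace it as follows.

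- Fix in advance which set of sites is primary, and always report results both for all sites and for non-CEB sites only. All sites is the simplest choice, but any CEB bias then stays in the primary result and the Conflicts of Interest statement needs rewording to match. Non-CEB sites as primary fits that statement, at the cost in precision shown in Step 3.
- Replace the t-test with an estimate of the CEB versus non-CEB difference and its 95% CI, from age-adjusted site means. A model with orthodontist or site as a random effect and small-sample degrees of freedom is an alternative; it was not simulated here.
- Name the outcome compared.
- State that non-significance will not be read as no difference, and that the result will not decide which sites stay.

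The site-means method was checked. Without an age term, and with site sizes drawn from 22-60, type I error is 0.048-0.051. With adjustment by the pooled within-site age slope (20,000 trials, assumed age-outcome correlation 0.3, mean age gap 0 or 0.5 SD), it is 0.048-0.055.

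The cost is one reworded paragraph, one table and, if all sites are primary, the matching change under Conflicts of Interest. No new data are needed. The CI will be wide: unadjusted mean half-width over ICC 0.01 to 0.20 is 0.89-1.85 SD at 2v2, 0.50-1.04 SD at 3v3 and 0.33-0.69 SD at 5v5, and the age-adjusted runs give similar widths. At 1v1 it cannot be estimated, and only the results with and without the CEB site can be shown.

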**Precision Orthodontics: A Comparison of Custom vs Traditional
Bracket Treatment Efficiency**

NCT Number: NCT04266769

December 17, 2019

Proposed Investigational Testing

Precision Orthodontics: A Comparison of Custom vs Traditional Bracket Treatment Efficiency

Scope

LightForce Orthodontics' (LFO) investigational testing aims to target multiple investigations sites to examine treatment efficiency metrics using a completely digital and patient-specific bracket treatment system for the correction of malocclusions.

Hypothesis

A fully digital and custom treatment system will provide a more efficient treatment experience compared to standard bracket treatments within the associated orthodontist's experience.

Objective

Compare metrics of treatment efficiency from a traditional "one-size fits all" fixed appliance (FA) system to a fully digital and 3D printed FA system.

Proposed Testing

Significance

Standard orthodontic practices use injection molded stock (not custom; traditional) brackets based on pre-programmed prescriptions to treat all patients with a variety of malocclusions. As each patient's anatomy and malocclusion are unique, this one size fits all approach leads to multiple forms of inefficiencies within a treatment. LightForce Orthodontics offers a digital treatment planning platform and patient-specific 3D printed polycrystalline alumina brackets which combat these inefficiencies and provide a better treatment plan.

The proposed LFO technology receives a digital scan of the patient's anatomy into the treatment planning software where the teeth are digitally moved from their starting position to the desired finishing positions. Brackets are placed in locations which enable Andrews' Straight Wire Appliance (SWA) principles to obtain the final occlusion. Among others, SWA principles dictate that a

treatment is completed when the arch wire no longer has any bends to it. The software program then reconstructs the initial malocclusion with the brackets in the locations which provide the desired outcome. Thus, the orthodontist can begin a treatment knowing exactly where the teeth will end up.

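### Primary outcomes are not designated and correction is optional, so the plan does not rule out resting its efficiency claim on one uncorrected metric, with a favourable-direction error above 2.5%

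*Combined protocol and SAP*

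**What the plan says.** **Outcomes.** Statistical Analysis uses the plural, "The primary outcome measures are impacted directly by" age and orthodontist, but no section marks any metric as primary. Investigation Design & Participants introduces six bullets with "Efficiency metrics may include", so the list is open and unranked. One bullet, "Bonding/De-bonding appointment time length", can be counted as one metric or two.

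**Tests.** The outcome variables go into an ANCOVA controlling for age and orthodontist. Two optional layers follow: "Multiple pair wise comparisons may be conducted (t-tests) to determine significant differences between groups" and "Multivariate linear regressions may also be used to examine differences in the treatment groups". The threshold is the same throughout: "All statistical tests will be two-sided with a p-value of 0.05 for statistical significance".

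**Multiplicity.** The only provision is "Bonferroni corrections may be conducted to prevent the introduction of Type 1 errors". No family of tests is defined. The sentence follows the one on pairwise comparisons, so it may concern only those and not the set of metrics.

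**Claim.** The Hypothesis is one directional statement: "A fully digital and custom treatment system will provide a more efficient treatment experience compared to standard bracket treatments". The Objective, by contrast, speaks of comparing metrics. No section gives a success rule, an order of testing or a requirement that all metrics succeed.

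**Sample size.** Investigation Design & Participants asks for at least 22 patients at each site for 90% power at a 5% level. It names no outcome, effect size, standard deviation or test.

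**The concern.** There is one overall claim, several candidate outcomes, a common threshold and a correction that may or may not be used. An analyst could follow this text to the letter and still decide, with the p-values in view, which metric supports the claim and whether to correct. A correction that can be taken up or dropped at that stage does not control error.

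At stake is the meaning of the nominal level for the study's main conclusion. If one significant metric in the favourable direction is enough, the chance of wrongly concluding that the custom system is more efficient is no longer the error of a single test.

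**Working it through.** **1. The plan's own figure.** The 22 per site can be neither reproduced nor refuted, because no effect size, standard deviation or test is given. Solving the t-test power equation for 90% at two-sided 0.05 with n = 22 gives a standardized effect of 1.0005 (two groups of 22) or 0.725 (one sample against a fixed figure). Both designs are assumptions; the documents do not state 22 comparator records per site. An unsplit 5% fits one test, or each metric taken separately. The sentence makes no visible allowance for a corrected family.

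**2. Inputs for the error rate.**
- Level per test: two-sided 0.05, hence 0.025 in the favourable direction (Statistical Analysis).
- Direction: the claim is of greater efficiency (Hypothesis), so a significantly worse metric cannot support it.
- Number of primaries k: not stated. The plural implies at least two; the list has six bullets, none marked primary. I take k = 2, 3 and 6.
- Correlation ρ between metrics: not stated. I take 0, 0.5 and 0.9, equal for all pairs.
- Condition: one significant metric in the favourable direction is enough, and no correction is applied.

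**3. Formulas, with no true difference on any metric.**
- Independent metrics, favourable direction: 1 − 0.975^k.
- Equal correlation ρ, normal test statistics: 1 − ∫ φ(u) Φ((1.96 − √ρ·u)/√(1−ρ))^k du, by numerical integration.
- Independent metrics, either direction: 1 − 0.95^k.

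**4. Results.** For independent metrics in the favourable direction: 1 − 0.975² = 0.0494; 1 − 0.975³ = 0.0731; 1 − 0.975⁶ = 0.1409.

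| k | Favourable, ρ = 0 | ρ = 0.5 | ρ = 0.9 | Either direction, ρ = 0 |
|---|---|---|---|---|
| 1 | 2.5% | 2.5% | 2.5% | 5.0% |
| 2 | 4.9% | 4.5% | 3.5% | 9.8% |
| 3 | 7.3% | 6.3% | 4.2% | 14.3% |
| 6 | 14.1% | 10.4% | 5.4% | 26.5% |

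For two metrics the favourable-direction error cannot exceed 2 × 2.5% = 5% at any correlation. Every favourable entry for k of two or more is above 2.5%; the excess vanishes only at correlation 1.

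**5. The other success rules.** If all metrics had to succeed, the favourable-direction error would be at most 2.5%, since the claim would then need any given null metric to be significant. If each metric is reported on its own and no overall claim is drawn, 5% holds for each.

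**6. Effect of a mandatory correction.** Bonferroni thresholds are 0.05/2 = 0.025, 0.05/3 = 0.0167 and 0.05/6 = 0.0083. With six independent metrics the either-direction familywise error is 1 − (1 − 0.00833)⁶ = 4.9%.

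At the effects in step 1, power per metric (noncentral t) at one site falls from 90% to 84% (two-sample) or 83% (one-sample) for k = 2, and to 71% or 68% for k = 6. With two sites pooled and k = 6 it is about 97% on either reading. Covariate effects and between-site variation are ignored.

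**The case against.** The strongest reply is that the Objective is to compare metrics, so the study reports each metric on its own and 5% holds for each. That is a fair reading of the Objective, and under it there is no familywise error to control. It does not dispose of the Hypothesis, which is a single overall claim with no rule linking it to the metrics.

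Second, the plan does mention Bonferroni. If it were applied across the metrics, the problem would be gone. But its use is optional and its scope undefined.

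Third, the size is easily overstated, and here the objection stands in several respects:
- A reader might infer that the plan allows any single metric to carry the claim. It does not say so. It is silent, and silence leaves that possibility open without granting it.
- A reader might infer an error of 26.5%, from six independent tests in either direction. That counts results showing the custom system to be worse, and it treats all six bullets as primary, which no section does.
- A reader might infer that 5% is always breached. With two primaries it cannot be in the favourable direction, and with three at correlation 0.9 the figure is 4.2%.
- The metrics are probably linked. The Significance section says that each bracket replacement lengthens treatment, which ties repositioned brackets to treatment length. That argues against taking independence as the main case, though no correlation is given.

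**Conclusion.** The point holds in a conditional form. The plan leaves the primary outcomes undesignated, the correction optional and the success rule unstated. If one uncorrected metric is allowed to carry the efficiency claim, the error of that claim rises from 2.5% to about 3.5–4.9% with two metrics, 4.2–7.3% with three and 5.4–14.1% with six, over correlations from 0.9 down to 0. These ranges rest on assumed numbers of metrics, equal correlations and normal test statistics. They are not ceilings, because the list is open and the optional t-tests and regressions are not counted.

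The documents do not support calling the study underpowered on this ground. The power sentence gives no effect size and does not say whether it refers to a per-site or a pooled analysis, and pooling even two sites would more than absorb a six-fold Bonferroni correction at the implied effects. The point should be fixed: it bears on the main conclusion and needs only wording.

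**What to change.** Make these changes before any comparison data are analysed.

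1. Name the primary metric or metrics from the list in Investigation Design & Participants, and count bonding and de-bonding time explicitly as one metric or two. The choice is the sponsor's.
2. Replace the optional Bonferroni sentence in Statistical Analysis with one mandatory rule:
   - (a) a Bonferroni or Holm adjustment across the named primaries at overall two-sided 0.05. This is the smallest edit and keeps several primaries; or
   - (b) one primary metric at two-sided 0.05, with the remaining metrics either Holm-adjusted and tested only if the primary is significant, or declared exploratory.
3. State that t-tests and regressions other than the specified primary analysis are exploratory. The exception matters because such a test might itself be chosen as the primary analysis.
4. State which outcome, which alpha and which analysis, per site or pooled, the power sentence refers to.

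The cost is protocol and SAP wording. Under (a) each primary faces a stricter threshold; if the power sentence is meant per site and per corrected metric, the sample size would have to be rechecked. Under (b) the primary keeps its full 0.05 and secondary claims are weaker.

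This does not by itself secure the 5% level. The form of the comparator data, the removal of site data after a significant difference between executive-board and other investigators, and the discretionary exclusion of outliers are separate issues.
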